ART	Antiretroviral therapy
AUDIT-C	Alcohol Use Disorders Identification Test – Consumption
CRF	Case report form
Grade 3/4 hepatotoxicity	ALT or ALT >3 x ULN and symptoms (nausea, vomiting, jaundice, or fatigue) OR ALT or AST >5 x ULN
NIAAA heavy drinking	Men: ≥ 4 drinks/day or ≥ 14 drinks/week; Women: ≥ 3 drinks/day or ≥ 7 drinks/week
INH	Isoniazid
IPT	Isoniazid preventive therapy
EMM	Electronic medication monitoring
PEth	Phosphatidylethanol
TST	Tuberculin skin test
ULN	Upper limit of normal

Alcohol users are considered at high risk for INH-related hepatotoxicity, based on an early study of IPT in which any and daily alcohol use were associated with 2- and 4- fold increases in toxicity rates, respectively.⁴⁵ However, the high rates of toxicity in this study have since been questioned.⁴⁶ Only a handful of studies since this 1978 publication have reported INH-related toxicity stratified by alcohol consumption level, and the findings of these subsequent studies have been mixed.^{26,47-51} Thus, data are urgently needed on the safety and tolerability of TB preventive therapy in HIV-infected drinkers to inform worldwide guidelines.⁵²

Adherence to TB preventive therapy among drinkers on ART is unknown. Among those with HIV, alcohol use has been consistently associated with reduced ART adherence,^{22,53,54} and we ([name]) and others have found that alcohol use is associated with discontinuation of active TB treatment.^{23,48,55} Reports of adherence to IPT among all comers range widely, from 19-96%.^{52,56} While completion of 9-months of IPT in a study of persons with HIV in Uganda was 34%,⁵⁶ several studies in HIV-infected persons have shown good completion rates (82%-87%), with the highest rates among those on ART.^{41,57-59} The addition of IPT to an established pill taking routine may be feasible, but adherence to and completion of TB preventive therapy among HIV-infected drinkers on ART is not known.

Valid measurement of medication adherence is critical to evaluating IPT. A key component of the scale up of TB preventive therapy for persons with HIV will ultimately be medication adherence. Self-reported adherence measures have limitations,⁶⁰⁻⁶³ especially in settings in which socially desirable responses are likely to be high. This problem was recently illustrated by the lack of efficacy of pre-exposure prophylaxis for HIV in a large trial, due to patients' misreporting taking the prescribed antiretrovirals.⁶⁴

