C.3.4 Enrollment – Eligibility screening and baseline study activities. Participants will initially be recruited from the Uganda ARCH cohorts, in which participants have given permission for re-contact for further study. Of the 465 current drinkers recruited in these cohorts, we estimate that we will be able to contact 75% (N=349), and that 60% of those will meet eligibility criteria (n=209). The remaining participants will be recruited from persons reporting any alcohol use on the AUDIT, approximately 25% of clinic patients,¹⁰⁹ which is routinely administered at initial ISS Clinic visit. We will also recruit patients who report no prior year alcohol use for the abstainer group. We will review the EMR for potential participants and those that meet preliminary study eligibility (i.e. age, on ART for 6 months) will be invited to meet with a research assistant to determine further eligibility. If further eligibility is established, the research assistant, a licensed clinical officer, will seek informed consent for further screening to rule out active TB, existing liver disease, and to assess TST status (Figure 1). A blood draw for ALT/AST testing will be performed, a TST will be placed, and if the participant reports symptoms of possible active TB (cough >24 hours, fever, weight loss, night sweats), further tests (chest X-ray and sputum collection for acid fast bacilli [AFB] stain and Xpert MTB/RIF assay) will be conducted. Those with abnormal chest X-ray results or a positive AFB or Xpert test will be brought to the MRRH TB clinic per hospital protocol. Patients will be asked to return in 2 days for TST reading, informed consent will be requested if active TB has been ruled out and TST is positive. After informed consent is obtained, the baseline visit will include study questionnaire completion, blood draw, and medication dispensing.

Aim 1: To examine the safety and tolerability of 6H for HIV-infected drinkers, measured by hepatotoxicity. Our main aim is to estimate safety overall among drinkers (primary) and by level of drinking (secondary). We will additionally compare safety and tolerability by level of drinking in secondary analyses.

Aim 2: To estimate the level of adherence to TB preventive therapy, overall among drinkers (primary), by month on therapy. Secondarily, we will estimate adherence by drinking level and compare adherence levels across drinking levels. We hypothesize that adherence will be highest among non-drinkers.

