C.3.5 Intervention. The study intervention will include a single arm given (1) 6H: 300 mg INH daily for 6 months. All participants will also receive 25 mg pyridoxine (vitamin B-6) daily for the treatment duration to reduce the risk of INH-induced peripheral neuropathy.¹¹¹ Patients will be encouraged to continue taking all other concurrently prescribed drugs (i.e., ART and cotrimoxazole). Patients will receive adherence advice, advice to avoid hepatotoxic substances (e.g. acetaminophen, alcohol, herbal medicines), instructions on monitoring side effects, phone numbers for contacting the medical staff in case of serious side effects, and instructions on using the EMM bottle like a regular medicine bottle. The pills will be dispensed at the pharmacy where the participants receive their ART.

C.3.6 Follow-up study visits. Assessments for toxicity will occur week 2 and months 1 through 7 (Table 3). A clinical officer will screen for symptoms of hepatotoxicity and other side effects using a Case Report Form (CRF) based on the TEMPRANO ANRS adverse event grading⁶ and perform ALT/AST testing. Treatment will be stopped if a patient develops a Grade 3/4 toxicity, as determined by the study physician. In addition, the monthly study visits while on medication will include pharmacy pill counts, EMM data downloads, and brief surveys on alcohol use and adherence. Hair collection will occur at 3 and 6 months. Blood collection will occur at baseline (for PEth, CD4 cell count, HIV viral load, and repository storage), 3 and 6 months, and every 6 months thereafter. Participants will also be given a card with phone numbers to contact the clinical staff if side effects occur between study visits; if side effects occur, participants will be asked to come in for additional ALT/AST testing and follow-up. These calls and visits will also be recorded in a CRF. All CRFs will be reviewed weekly by the study physician. Screening for symptoms for active TB, and sputum testing and chest X-ray if symptoms are reported, will occur at every follow-up visit, including those after the completion of the trial. High retention will be maintained as in our prior studies using follow up phone calls, alerts when patients come to the ISS clinic, and home visits when needed.

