C.3.7 Data management. Data management and quality assurance will be jointly led by the UCSF and the BU Data Coordinating Center (DCC). As in the previous studies, tracking information will be entered into a database which will generate reminders for follow-up visits. The tracking database will also be used to automatically randomize patients to study arms. The questionnaire data, brief assessments, laboratory results, and the CRF data will be entered directly into a laptop computer in Uganda while offline, and later uploaded to a secure server at UCSF. The EMM adherence data will be uploaded weekly to a secure website, cleaned, and merged with the other study data. All data will undergo weekly checks for completeness and range criteria.

C.3.8 Measurements.

Safety and tolerability. Safety will be assessed by the occurrence of a Grade 3/4 hepatotoxicity at any time during the assigned treatment period. Lack of tolerability will be defined as any treatment discontinuation prior to completion of the prescribed course due to side effects or ALT/AST elevations.

Adherence. We will measure medication adherence using EMM, pharmacy pill count, self-report, and INH concentration in hair. While there is no gold standard for determining medication adherence, EMM adherence has been highly predictive of undetectable HIV viral load¹¹²⁻¹¹⁴ is considered the reference standard,^{62,112,115,116} and therefore will be our primary measure of adherence. EMM adherence will be defined as the number of pill bottle openings (no more than 1 per day counted)¹¹³ divided by the number of prescribed doses over the study period. Adherence to vitamin B-6, which will be provided in a separate bottle, will not be part of the adherence measurement.

Self-reported adherence measures will include the visual analog scale (VAS) which asks the patient to identify their past month percent adherence on a visual scale that ranges from 0 to 100%, and the Self Rating Single Item (SRSI) adherence scale,^{117,118} which asks participants to rate their ability to take their medications as prescribed over the past month.¹¹⁹ Both of these measures are brief¹¹⁸ and are strong predictors of viral suppression.¹¹⁸ Lastly, we will collect hair samples at 3 months and 6 months, and will measure the INH concentration (ng/mg) in the hair.

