Alcohol consumption. Heavy drinking will be defined as either PEth \geq 50 ng/mL or AUDIT-C positive (\geq 3 for women, \geq 4 for men). The AUDIT-C will be modified to cover the prior 3 months. By combining two highly specific measures, we will increase the sensitivity for detecting heavy alcohol use over using each measure alone, as in our previous analyses of heavy alcohol use by persons with HIV in Uganda.^{81,82}

We will collect self-reported measures of alcohol use at baseline using the AUDIT-C and the CAGE,¹²⁰ which are readily available for use in clinical practice. For analyses that examine level of drinking, we will categorize

the scores as low risk drinking, (women: AUDIT-C 0-2; men: AUDIT-C 0-3), heavy drinking (women: AUDIT-C 3-5; men: AUDIT-C 4-5), and very high risk drinking (AUDIT-C ≥ 8).¹²¹ The corresponding cutoffs for the CAGE will be scores of 0, 1, and 2-4.¹²² We will additionally measure alcohol consumption using tools that are not dependent on standardized drink volume or concentration, e.g. money spent drinking, level of intoxication, and PEth level, as in our previous studies.¹⁰¹

Covariates. Covariates measured at baseline will include gender, age, body mass index (BMI), CD4 cell count, HIV viral load, ALT/AST, active hepatitis B viral infection (HBsAg), symptoms of depression,¹²³ smoking, nicotine dependence,¹²⁴ and duration on ART – also recently added on baseline platelet count, FIB-4 score, and eGFR. Covariates measured at baseline and follow-up will include current ART regimen, and the VAS and SRSI for self-reported ART adherence.

Table 3. Schedule of study visits and activities.

	Eligibility	Baseline	Week 2	Month 1	Month 2	Month 3	Month 4	Month 5	Month 6	Month 7	Follow-up
Initial eligibility determined, ALT/AST and TST testing. Chest X-ray and sputum collected if symptoms of active TB are reported.	X										
Enrollment/ baseline: Study interview, blood draw, medication dispensing		X									
Toxicity assessment (side effects and ALT/AST testing)			X	X	X	X	X	X	X	X	
Medication refill, pharmacy pill count, and EMM data download, and brief alcohol and adherence assessments			X	X	X	X	X	X	X		
Hair collection for INH concentration						X			X		
Follow-up: Study interview, blood draw, and screening for active TB						X			X		X

C.3.9 Statistical analyses for Aim 1.

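### No hepatotoxicity symptom check is planned before the first dose, so a symptom that pre-dates treatment can turn an on-treatment ALT/AST rise to 3–5x ULN into a primary Grade 3/4 event

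*Combined protocol and SAP*

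**What the plan says.** **Endpoint.** Table 1 defines Grade 3/4 hepatotoxicity as "ALT or ALT >3 x ULN and symptoms (nausea, vomiting, jaundice, or fatigue) OR ALT or AST >5 x ULN". I read the repeated ALT in the first limb as ALT or AST. The definition does not require the symptom to be new, worse than before or related to the drug. C.3.8 makes this the safety outcome: "Safety will be assessed by the occurrence of a Grade 3/4 hepatotoxicity at any time during the assigned treatment period".

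**When symptoms are recorded.** C.3.6 states: "Assessments for toxicity will occur week 2 and months 1 through 7". The clinical officer's symptom form is described there, under follow-up visits. In Table 3 the toxicity row is marked from Week 2 to Month 7, and its Eligibility and Baseline cells are empty.

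**What happens before dosing.** ALT/AST is measured at screening, and values above 2x ULN exclude (C.3.3). The symptom screen in C.3.4 covers cough, fever, weight loss and night sweats. After consent, "the baseline visit will include study questionnaire completion, blood draw, and medication dispensing". The baseline covariates in C.3.8 include ALT/AST and depressive symptoms, but none of the four Table 1 symptoms.

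**Why there is no control arm.** C.3.2, item 2, argues that an untreated group is not needed because baseline testing will show the background level of ALT/AST elevations. It says nothing about background symptoms.

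**The concern.** The endpoint has an enzyme part and a symptom part. The enzyme part has a pre-dose value; no pre-dose value is planned for the symptom part. Between 3x and 5x ULN, the symptom alone decides whether a participant counts.

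Take two participants who enter at 1.9x ULN and rise to 3.1x ULN on treatment. One has had fatigue for a long time and the other has not. Under Table 1 the first is a primary event and the second is not, although the enzyme course is the same. The planned data contain no pre-dose record showing that the fatigue came first.

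In a controlled trial, background symptoms would appear in both arms. Here the incidence among drinkers stands alone, is set beside published rates (C.3.9), and is compared across drinking levels. The expected count is so small that one or two such events would be visible in the result.

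**Working it through.** **1. The plan's own figures (C.3.9, sample size).**
- Evaluable drinkers: 200 × 0.90 = 180.
- Expected events: 180 × 0.026 = 4.68, which the plan rounds to about 5.
- Clopper-Pearson 95% interval for 5/180: 0.91% to 6.36%, length 5.46 points. This reproduces the stated 0.9% to 6.4% and 5.5%.

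**2. Weight of one event.** 1/180 = 0.56 percentage points, and 0.56/2.6 = 0.21, about one fifth of the expected rate.

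**3. What reclassification would do.** Suppose 5 events are observed and 2 of them rest only on a symptom that was there before dosing.
- Table 1 count: 5/180 = 2.8% (0.91% to 6.36%).
- New-or-worse count: 3/180 = 1.7% (0.35% to 4.79%).

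The 2 is an illustration; the documents give no basis for any particular number.

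**4. Range under assumptions.** Let q be the share of drinkers who reach 3–5x ULN on treatment without a new symptom, and s the share of these with a pre-existing listed symptom. Extra events = 180 × q × s. The documents give neither input. The nearest figure for q is the 7.6% of 169 cohort members with elevations of 2–5x ULN (C.2). That band includes 2–3x ULN and people whom this trial would exclude, so I use it only as the top of the range.

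| q | s | Extra events | Expected rate, (4.68 + extra)/180 |
|---|---|---|---|
| 2% | 5% | 0.18 | 2.7% |
| 5% | 10% | 0.90 | 3.1% |
| 5% | 20% | 1.80 | 3.6% |
| 7.6% | 30% | 4.10 | 4.9% |

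The table also assumes that the planned 2.6% contains no such events. The span runs from negligible to nearly double, so it shows sensitivity and does not estimate the bias.

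**5. What the planned visits can and cannot resolve.**
- *Symptom absent at week 2, present later with the enzyme rise:* there is an earlier symptom-free record, so the symptom is recent.
- *Symptom present at week 2 with enzymes below 3x ULN, rise later:* the symptom came before the rise, but it may have begun before dosing or in the first two weeks on isoniazid.
- *Symptom and rise both present at week 2:* no planned earlier record exists for comparison.
- *Month 7, after a 6-month course taken on schedule:* a symptom that persists off drug points to a background cause. One that resolves points the other way. Neither is proof.

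**The case against.** **The baseline questionnaire may already ask.** Its items are not listed, and the covariate list need not be exhaustive. This stands as a limit: a reader might infer that symptoms are never asked about before dosing, but the documents support only that no such assessment is planned in them. If the items are there, the change reduces to saying so and marking Table 3.

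**The data can be repaired later.** One might infer that the gap is irreparable once participants are enrolled. That is too strong. As step 5 of the working shows, the week 2 to month 7 records resolve some cases. Onset before the first dose versus onset in the first two weeks remains unresolved.

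**A symptom alone cannot make an event.** Correct. Entry requires ALT/AST not above 2x ULN, so every event on the symptomatic limb also needs an on-treatment rise above 3x ULN. The plan counts events that meet a fixed definition and does not promise attribution to the drug. For that reason the Table 1 count should stay primary.

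**The study physician judges Grade 3/4 and reviews the forms weekly (C.3.6).** This may filter some cases. The determination is stated for stopping treatment, however. No rule on new versus old symptoms is given, and no pre-dose record is planned to judge against.

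**Bias across drinking levels, and tolerability.** A reader might infer that the comparison by drinking level is biased towards harm from alcohol. That needs background nausea or fatigue to be more common in heavier drinkers, and the documents give no figure. Nor does tolerability share the same mechanism: it requires discontinuation because of side effects or enzyme elevations, and the mere presence of a symptom is not enough.

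**Conclusion.** The point holds as a gap in measurement that should be closed. It does not make the primary analysis invalid. No pre-dose record of the four Table 1 symptoms is planned in the documents, the definition does not ask whether a symptom is new, and the single-arm rationale covers background enzymes only. Any misclassification of this kind adds to the overall count among drinkers and so overstates harm. It is confined to rises of 3–5x ULN.

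The size cannot be derived from the documents. The firm figure is the weight of each event: 0.56 percentage points, about one fifth of the expected 2.6%, given 180 evaluable drinkers. A reader might take the upper rows of the assumed range as evidence that the rate could nearly double; those rows rest wholly on assumed inputs and do not support that conclusion.

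**What to change.** 1. In Table 3, mark the side-effect part of the toxicity form at Baseline, and state in C.3.4 that it is completed before the first dose. Use the same form and grading as at follow-up, so that grades can be compared.
2. In C.3.9, keep the Table 1 count as the primary result. Add a prespecified sensitivity count in which the symptomatic limb requires a symptom that is new or of higher grade than at Baseline.
3. Report the symptomatic limb above 3x ULN and the limb above 5x ULN separately, overall and by drinking level.

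The treatment-stopping rule is not changed by any of this.

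**Cost.** A few minutes per participant at a visit that already takes place, and one extra table. C.3.4 describes the research assistant who seeks consent as a licensed clinical officer, so suitable staff are in place. The sample size and planned interval do not change. Anyone already dosed will have no pre-dose value; report their number, and classify them in the sensitivity count by a rule fixed in advance.

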The target population will be HIV/TB-infected men and women who are either current drinkers (past 3 months, n=200) or non-drinkers (no alcohol in the past year, n=100), who meet screening criteria (i.e. ≥ 18 years old, on ART, TST positive, no history of prior active TB, live within 2 hours travel time of the study site), and are patients of the Mbarara Regional Referral Hospital (MRRH) Immune Suppression Syndrome (ISS) Clinic. This study will build on the foundation of the Uganda ARCH cohort, including its predecessor cohort as well. We will contact Uganda ARCH study participants (which included drinkers and non-drinkers) to determine their current eligibility for the proposed study. Those who are eligible and interested will be enrolled in the study of TB preventive therapy and receive continued follow-up as part of the Uganda ARCH cohort within the URBAN ARCH consortium. We will enroll additional participants recruited from the ISS Clinic, as needed, to meet our enrollment targets. A screening phase will include blood testing to test liver enzymes (ALT and AST) to rule out patients with elevations ($>2x$ the upper limit of normal [ULN]), and to rule out active TB (symptom screening, and if symptomatic: AFB and Xpert MTB/RIF testing and chest X-ray if not pregnant). Once considered eligible for the study, INH and pyridoxine (vitamin B6) will be dispensed and the study will include regular assessments of hepatotoxicity and other side effects, measures of medication adherence, assessment of drinking, and collection of dried blood spots (DBS) for PEth and small hair samples (approximately 100 hair fibers) for PEth and INH concentration, respectively. After the course of INH (6 months, daily) is completed, study participants will participate in twice yearly study visits as part of the continued cohort. The follow-up cohort study visits will include a survey, symptom assessment and follow-up testing as needed to detect active TB, and blood collection for DBS for PEth, and storage in the URBAN ARCH repository. Baseline blood testing will also include tests for hepatitis B surface antigen, confirmation of HIV status, CD4 cell count, and HIV viral load.

NIH-REQUIRED PROGRESS REPORT

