[name] and several trainees from the University of California San Francisco (UCSF) and the Mbarara, Uganda, University of Science and Technology (MUST) leveraged the Uganda ARCH cohort into newly funded alcohol/HIV research studies and fellowships. [name] received a prestigious K24 Mid-career Investigator Award in Patient-Oriented Research (NIA K24AA022586) to build her research and mentoring program in HIV/alcohol comorbidity, a UCSF Center for AIDS Research (CFAR) Established Investigator pilot award, and an award from the US Department of Defense. Three junior investigators ([name], [name], and [name]) received UCSF CFAR pilot awards, and [name] received 2 training awards, allowing her to spend 4 months learning research methods and writing in San Francisco.

C. APPROACH

C.1 The proposed study builds on existing collaborative relationships. This research will be conducted in the context of the URBAN ARCH Consortium, leveraging the infrastructure developed over the past five years of the Uganda ARCH cohort as a collaborative effort between UCSF, Boston University (BU), Boston Medical Center (BMC), and MUST. The team includes international experts in alcohol and HIV epidemiology and biomarkers of alcohol use ([name]), clinical research in persons with HIV in Uganda ([name]), TB outcomes in resource limited settings ([name]), decision analytic modeling ([name]), clinical trial design and analysis ([name]), and hair drug concentration ([name]). Consultants include world experts in clinical trials of TB medications ([name]) and HIV/substance use research ([name]).

C.2 Preliminary data for this application

Little evidence of liver damage due to alcohol use. We ([name]) conducted liver enzyme testing in 169 HIV-infected participants in the Uganda ARCH cohort at the baseline visit. A small proportion, 7.6%, had Grade 1/2

Table 2. Baseline characteristics of the Uganda ARCH cohorts (U01 AA020776 and R01 AA018631), n=751.

Male	41%
Age, median (Interquartile range [IQR])	31 (26-39)
CD4 cell count, median (IQR) cells/mm³	462 (330-638)
Log HIV viral load	3.79 (3.00-4.39)
Self-reported alcohol use, prior 3 months	62%
Among current drinkers (prior 3 months, n=465)	
Self-reported heavy drinking: AUDIT-C+	52%
PEth >=50 ng/ml	59%
Heavy drinking (AUDIT-C+ or PEth ≥50 ng/ml)	73%
PEth level, ng/ml, median (IQR)	75.8 (16.0-274.0)

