(5) The eligibility criterion for the proposed study is current (prior 3 month) drinking OR non drinking in the prior year, while the WHO recommendations refer to “regular and heavy alcohol consumption”. We will use “current drinking” because we have found that while half of current drinkers report heavy drinking by the AUDIT-C criteria (52%), a large proportion of current drinkers (21%) have high PEth levels (≥ 50 ng/ml) but do not report heavy drinking (Table 2, above). Thus, an eligibility criterion of current drinking will allow us to examine toxicities among drinkers who do not fully report their level of drinking so that future guidelines can account for under-reporting of drinking.

C.3.3 Study setting and eligibility. This study will be conducted in the Immune Suppression Syndrome (ISS) HIV Clinic of the Mbarara Regional Referral Hospital (MRRH) at MUST, the site of the Uganda ARCH. There are over 12,000 active patients at the ISS Clinic. The ISS Clinic and pharmacy use electronic medical records (EMR) via the Open Medical Record System (OpenMRS). Eligibility criteria will be: ISS clinic patient age ≥ 18 , living within 2 travel hours of the clinic, fluent in Runyankole or English, on ART, and self-reported alcohol consumption in the prior 3 months or abstainer. Exclusion criteria will be as follows: plans to move in the coming 6 months, on nevirapine (NVP, an ART drug that is declining in usage due to high risk for hepatotoxicity), history of active TB, current active TB, prior TB preventive therapy, and ALT or ALT elevation ($>2x$ ULN).

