Primary analysis: Safety. The focus of this aim is the evaluation of safety among drinkers overall (primary) and by drinking levels (secondary). Thus the primary analysis set will be all participants who receive at least one dose of TB preventive therapy who are current drinkers. We will report the incidence of Grade 3/4 hepatotoxicity at any time during prescribed treatment along with 95% exact binomial confidence intervals (CIs).

Secondary analyses: Safety and tolerability will be estimated by level of alcohol use at baseline and during treatment. To examine safety and tolerability by alcohol consumption prior to treatment, we will report hepatotoxicity and treatment discontinuation stratified by level of drinking (heavy alcohol consumption, current but not heavy drinking, no drinking) at baseline. Fisher's exact test and exact logistic regression models adjusting for gender, hepatitis B co-infection, Cd4 cell count and/or viral suppression will be used to compare safety outcomes across drinking levels. To inform clinical practice, we will also report the outcomes by self-reported alcohol consumption levels using the AUDIT-C and the CAGE. We will also examine toxicity by level of PEth, using recently suggested PEth cutoffs. We will use generalized estimating equation logistic regression models to examine whether drinking level during the treatment period impacts safety and tolerability outcomes.

Secondary analysis: Comparison of hepatotoxicity rates to previous studies. We will also compare estimates and 95% CIs to those reported in published studies of TB preventive therapy in those with HIV, which found hepatotoxicity rates of 0.3-5.5%.

Sample size justification. We anticipate a total of 200 drinkers will be enrolled into the current study. Based on the Uganda ARCH cohort retention, we expect 90% 6-month study visit retention resulting in N=180 evaluable participants. We expect that the proportion of participants with any Grade 3/4 hepatotoxicity within the treatment period will be approximately at the midpoint of the range of toxicity rates published previously, i.e. 2.6%. Given this, we would expect approximately 5 safety events, and the length of a 95% exact binomial CI around the estimate would be 5.5%, (i.e. 0.9% to 6.4%).

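### In the secondary three-group comparisons, a self-reported abstainer with quantifiable baseline PEth below 50 ng/mL by default stays in the non-drinker reference group

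*Combined protocol and SAP*

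**What the plan says.** **Who is a non-drinker.** The Study Design Overview enrols "either current drinkers (past 3 months, n=200) or non-drinkers (no alcohol in the past year, n=100". C.3.3 admits people with "self-reported alcohol consumption in the prior 3 months or abstainer". C.3.4 adds: "We will also recruit patients who report no prior year alcohol use for the abstainer group". None of these sets a PEth condition.

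**Where PEth enters the grouping.** C.3.8 begins "Heavy drinking will be defined as either PEth" and gives the rule as 50 ng/mL or more, or a positive AUDIT-C. The separate AUDIT-C scheme in C.3.8 starts with "low risk drinking, (women: AUDIT-C 0-2; men: AUDIT-C 0-3", so it has no class for non-drinkers.

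**How the groups are used.** C.3.9 analyses safety and tolerability "stratified by level of drinking (heavy alcohol consumption, current but not heavy drinking, no drinking) at baseline". C.3.10 uses the same three levels for EMM adherence and for INH concentration in hair. The Specific Aims hypothesise that adherence is highest in non-drinkers. They call the comparison across levels secondary, although it sits in the primary-analysis paragraph of C.3.10.

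**What PEth is for.** The Specific Aims and the Study Design Overview describe drinking level as self-report supplemented by PEth, and the Innovation section says this is to prevent misclassification. C.3.6 collects PEth at baseline. C.3.9 also plans a toxicity analysis by PEth level.

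**The concern.** The plan expects under-reporting and has a biomarker to detect it, but the written rule uses that biomarker only to identify heavy drinking. For someone who reports no past-year alcohol, a quantifiable value below 50 ng/mL changes nothing. That person is not heavy and is not a self-reported current drinker, so the reference group is what remains.

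Recent drinkers in the reference group move its mean or event rate toward that of the drinkers. The contrasts at stake are heavy and non-heavy drinkers against non-drinkers for safety, tolerability, EMM adherence and hair INH. The adherence contrast matters most, because it carries a stated directional hypothesis.

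**Working it through.** **1. Group rules side by side, for a person reporting no past-year use**

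| Baseline PEth | Heavy rule (C.3.8) | Reported current drinking (C.3.3) | Resulting group |
|---|---|---|---|
| Not quantifiable | no | no | no drinking |
| Quantifiable, below 50 | no | no | no drinking, by default |
| 50 or more | yes, on the literal wording | no | heavy; no sentence confirms it |

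The second row is the problem. The third needs only confirmation. Table 2 in C.2 reports "Heavy drinking (AUDIT-C+ or PEth ≥50 ng/ml" under the row "Among current drinkers (prior 3 months, n=465", but that describes an earlier cohort and is not an analysis rule.

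**2. The plan's own power figure**

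Inputs from C.3.9: 1% against 1% + 9.5 points = 10.5%, each group one third of 300 = 100, Fisher's exact test, alpha 0.05 (taken as two-sided; the plan does not say). Exact power is 0.807 and the detectable difference at 80% power is 0.094, so the stated 0.095 reproduces.

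**3. Hidden drinkers left in the reference group**

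The share x and their risk r are assumed. Reference rate = (1 − x) × 1% + x × r; comparison group 10.5%; 100 v 100.

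| r | x = 10% | x = 20% | x = 40% |
|---|---|---|---|
| 1% (plan's rate for lighter drinkers and abstainers) | 0.81 | 0.81 | 0.81 |
| 2.6% (plan's expected rate in drinkers) | 0.78 | 0.75 | 0.70 |
| 10.5% (upper bound) | 0.64 | 0.49 | 0.24 |

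At r = 2.6% the reference rate is 1.16, 1.32 and 1.64%, and the odds ratio falls from 11.6 to 10.0, 8.8 and 7.0. Misclassification is not the main limit on the safety contrast: at 2.6% v 1%, power is 0.02 even with perfect grouping.

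**4. Adherence**

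Let D be the true difference between non-drinkers and drinkers, and let hidden drinkers have a deficit of f × D. The observed difference is D × (1 − x × f). For x = 10, 20 and 40% the loss is 5, 10 and 20% of D at f = 0.5, and 10, 20 and 40% at f = 1.

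**5. Cost of excluding PEth-positive abstainers from the reference**

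Reference n = 90, 80 or 60. With equal standard deviations and 100 in the drinker group, the standard error ratio is √(1/100 + 1/n) / √(2/100) = 1.03, 1.06 and 1.15.

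Fisher power at 10.5% v 1%:
- 100 non-heavy: 0.82, 0.81 and 0.68, against 0.81 with all 100 in the reference.
- 54 non-heavy: 0.66, 0.68 and 0.59, against 0.71. The 54 is 200 × (1 − 0.73), using Table 2's 73% heavy.

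Power does not fall smoothly, because the test is discrete.

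**6. Moving them into the non-heavy group instead**

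At r = 1%, moving 20 people gives non-heavy v none power of 0.65 (120 v 80), against 0.81 if they stay. With 54 non-heavy it gives 0.49 (74 v 80), against 0.71. At the upper bound of 10.5% the order reverses: with 100 non-heavy, moving 20 gives 0.80, against 0.49 if they stay.

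**The case against.** Four points can fairly be made against this.

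- **The plan says drinking level is self-report supplemented by PEth.** Neither place that says so limits PEth to the heavy cut-off. This stands as a statement of intent, and it is why the finding is worded as a default. It supplies no rule for values below 50.
- **An abstainer at 50 or above is already heavy.** This stands. A reader might infer that the placement is undefined, but the rule in C.3.8 is unconditional and meant to raise sensitivity. One confirming sentence is enough.
- **Other analyses help.** The PEth-level toxicity analysis and the models with drinking level during treatment (C.3.9, C.3.10) do so in part. They do not change the baseline reference group, and no PEth-level analysis is written for adherence or hair INH.
- **The impact is assumed.** This also stands. A reader might take the statement in C.2 that over half of those with quantifiable PEth had denied drinking as the share of abstainers who drink. It is not: it conditions on a positive PEth, concerns prior-month use and comes from another study. C.2 also reports that self-reported use doubled once biomarker specimens were collected, as they are here, so denial may be less common.

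**Conclusion.** The point holds as a minor gap in the secondary analyses. By default, self-reported abstainers with quantifiable PEth below 50 ng/mL remain in the non-drinker group, which can bias the three-group contrasts toward no difference.

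The size cannot be fixed from the documents. It runs from no loss of power, if hidden drinkers carry the 1% rate, to a large loss only if they carry the full 10.5%. For adherence, the loss is the hidden share times the fraction of the drinkers' deficit that those people have.

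A reader might infer that the main safety result is compromised. It is not: on the natural reading, its analysis set is self-reported current drinkers, and the non-drinker group plays no part in it. The case for the change is correct classification, not a gain in power.

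**What to change.** 1. Keep the planned three-group comparisons, with the reference group set by self-report.
2. Pre-specify, for Aim 1 (safety, tolerability) and Aim 2 (EMM adherence, hair INH), the same contrasts with the reference limited to participants with no reported past-year use **and** baseline PEth below the assay's quantification limit. State that limit in the SAP. Remove PEth-positive abstainers from the reference without adding them to the non-heavy group.
3. Confirm in one sentence that a self-reported abstainer at 50 ng/mL or above is classed as heavy in the three-group analysis.
4. Confirm that the primary set is self-reported current drinkers, and that any abstainer classed as heavy is not counted in the overall estimate among drinkers.
5. Treat moving PEth-positive abstainers into the non-heavy group as a further sensitivity analysis at most. It dilutes that group when their risk is low, and the drinker strata then no longer add up to the overall drinker group.

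**Cost.** This is SAP wording only; baseline PEth is already collected. The reference group becomes smaller, with the loss of precision shown in step 5 of the working. PEth reflects roughly the previous 3 weeks (Background and Significance), so a negative result does not prove past-year abstinence and some misclassification will remain.
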